7 STUDY PROCEDURES AND ASSESSMENTS

7.1 Efficacy Assessments

7.1.1 Response Criteria Definitions

7.1.1.1 Acute Myeloid Leukemia Response Criteria

Response to treatment will be defined per modified criteria [Cheson et al, 2003] as outlined below.

- Complete Remission (CR)

For subjects to be classified as being in CR at a post-baseline visit, they must have bone marrow regenerating normal hematopoietic cells and achieve a morphologic leukemia-free state and must have an absolute neutrophil count (ANC) $\geq 1 \times 10^9/L$ and platelet count $\geq 100 \times 10^9/L$, and normal marrow differential with $< 5\%$ blasts, and they will be red blood cell (RBC) and platelet transfusion independent (defined as 1 week without RBC transfusion and 1 week without platelet transfusion). There must be no presence of Auer rods. There should be no evidence of extramedullary leukemia. The blast counts in peripheral blood must be $\leq 2\%$.

- Complete Remission with Incomplete Platelet Recovery (CRp)

For subjects to be classified as being in CRp at a post-baseline visit, they must achieve CR except for incomplete platelet recovery ($< 100 \times 10^9/L$).

- Complete Remission with Incomplete Hematological Recovery (CRI)

For subjects to be classified as being in CRI at a post-baseline visit, they must fulfill all the criteria for CR except for incomplete hematological recovery with residual neutropenia (ANC $< 1 \times 10^9/L$) with or without complete platelet recovery. RBC and platelet transfusion independence is not required.

- Composite Complete Remission (CRC)

For subjects to be classified as being in CRC at a post-baseline visit, they must either achieve CR, CRp or CRI at the visit.

- Complete Remission with Partial Hematologic Recovery (CRh)

For subjects to be classified as CRh at a post-baseline visit, if they have marrow blasts $< 5\%$, partial hematologic recovery ANC $\geq 0.5 \times 10^9/L$ and platelets $\geq 50 \times 10^9/L$, no evidence of extramedullary leukemia and cannot be classified as CR. The blast counts in peripheral blood must be $\leq 2\%$.

- Partial Remission (PR)

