7.1.1.2 Myelodysplastic Syndrome Response Criteria

Response to treatment will be defined according to the modified International Working Group response criteria [Cheson et al, 2006] as outlined below.

- Complete Remission (CR)

For subjects to be classified as being in CR at a post-baseline visit, they must have all of the following maintained for a minimum of 4 weeks:

- Bone marrow evaluation: $\leq 5\%$ myeloblasts with normal maturation of all cell lines
- Peripheral blood evaluation:
 - Hemoglobin ≥ 11 g/dL
 - Platelets $\geq 100 \times 10^9/L$
 - Neutrophils $\geq 1.0 \times 10^9/L$
 - 0% blasts in blood

- Partial Remission (PR)

For subjects to be classified as being in PR at a post-baseline visit, they must have all CR criteria if abnormal before treatment except the following for a minimum of 4 weeks:

- Bone marrow blasts decreased by $\geq 50\%$ over pretreatment but still $> 5\%$
- Cellularity and morphology not relevant

- Marrow CR

For subjects to be classified as being in marrow CR at a post-baseline visit, they must have all of the following for a minimum of 4 weeks:

- Bone marrow: $\leq 5\%$ myeloblasts and decrease by $\geq 50\%$ over pretreatment
 - Peripheral blood: if HI responses, they will be noted in addition to marrow CR

- Hematologic Improvement (HI)

Requires 1 measurement of the following maintained for at least 8 weeks without ongoing cytotoxic therapy:

- HI – erythroid:

- Hemoglobin increase of ≥ 1.5 g/dL
or
- For RBC transfusions performed for hemoglobin ≤ 9.0 g/dL: reduction in RBC units transfused in 8 weeks by ≥ 4 units compared to the number of units transfused in the 8 weeks prior to treatment
- HI – platelets:
 - For pre-treatment platelet count of $>20 \times 10^9/L$ platelet, absolute increase of $\geq 30 \times 10^9/L$
 - For pre-treatment platelet count of $< 20 \times 10^9/L$, platelet absolute increase of $> 20 \times 10^9/L$ and $\geq 100\%$ increase from pre-treatment level
- HI – neutrophils:
 - Neutrophil count increase of $\geq 100\%$ from pre-treatment level and an absolute increase of $> 0.5 \times 10^9/L$

- **Relapse after CR or PR**
Requires at least 1 of the following:
 - Return to pre-treatment bone marrow blast percentage
 - Decrement of $\geq 50\%$ from maximum response levels in granulocytes or platelets
 - Transfusion dependence or hemoglobin level ≥ 1.5 g/dL lower than prior to therapy

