9.1 Sample Size

Phase 1 (Dose Escalation)

The sample size for the dose escalation phase is not based on a statistical power calculation. The number of subjects enrolled will be dependent on the DLT incidence. The estimated number of subjects, a minimum of 6 evaluable and up to 18, should provide adequate information for the dose escalation and safety objectives of the study.

Phase 2 (Dose Expansion)

The sample size in phase 2 is up to 104 subjects per dose level. Each dose level may enroll up to 52 R/R AML subjects and up to 52 R/R higher risk MDS subjects. The response rate is monitored using the BOP2 design. For AML, with assumption of the efficacious CRc rate is 30% and the inefficacious CRc rate is 15%, the statistical power would be approximately 0.83 while controlling the type I error rate at 0.10. For MDS, with assumption of the efficacious CR + BM CR + PR rate is 25% and the inefficacious CR + BM CR + PR rate is 12%, the statistical power would be approximately 0.83, while controlling the type I error rate at 0.10.

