9.4.1.3 Phase 2 Expansion

The CRc rate for subjects with R/R AML and CR + BM CR + PR rate for R/R higher risk MDS are continuously monitored using the BOP2 design [Zhou et al, 2017]. The number of dose levels investigated during phase 2 will be based upon the data from phase 1. Initially, 12 subjects will be enrolled at each dose level for each disease type during stage 1 of BOP2. If the response rate does not meet the optimal stopping boundaries (see table below), then stage 2 will open and an additional 20 subjects may be enrolled during this stage. Combining the data from stage 1 and stage 2, stage 3 may be opened for an additional 20 subjects for a total maximum sample size of 52 for each disease type, if the response rate does not meet the optimal stopping boundaries (see table below). Otherwise, the enrollment at that dose level will be closed.

When the total number of subjects reaches the maximum sample size of 52, it may be concluded that ASP7517 is efficacious if the number of responses is greater than or equal to 12 and 10 for AML and MDS, respectively. The number of subjects in stage 1, stage 2 and stage 3 may be changed according to the optimized stopping boundaries.

Optimized Stopping Boundaries for AML	
Number of subjects treated	Stop if number of responses ≤
12	1
32	5

AML: acute myeloid leukemia

Optimized Stopping Boundaries for MDS	
Number of subjects treated	Stop if number of responses ≤
12	0
32	4

MDS: myelodysplastic syndrome

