12.6 List of Excluded Concomitant Medications

12.6.1 Concomitant Medications

The following list describes concomitant medications that are prohibited. This list should not be considered all inclusive. If there are concerns or questions about concomitant use of any drugs listed below, discussion with the medical monitor is strongly encouraged.

Drug Type	Generic Drug Name
Corticosteroids*	Dexamethasone Prednisone (Deltasone, Orasone, Predone, RAYOS, Sterapred, etc.)
Interferon/polyethylene-interferon	
Immunosuppressive Agents	Abatacept (Orencia, etc.) Adalimumab (Humira, etc.) Anajunra (Kineret, etc.) Azathioprine (Azasan, Imuran, etc.) Budesonide (Entocort EC, etc.) Certolizumab (Cimzia, etc.) Cyclosporine (Neoral, Sandimmune, SangCya, etc.) Etanercept (Enbrel, etc) Everolimus (Afinitor, Zortress, etc.) Golimumab (Simponi, etc.) Infliximab (Remicade, etc.) Ixekizumab (Taltz, etc.) Leflunomide (Arava, etc.) Mycophenolate (CellCept, Myfortic, etc.) Natalizumab (Tysabri, etc.) Prednisolone (Millipred, etc.) Rituximab (Rituxan, etc.) Secukinumab (Cosentyx, etc.) Sirolimus (Rapamune, etc.) Tocilizumab (Actemra, etc.) Tofacitinib (Xeljanz, etc.) Ustekinumab (Stelara, etc.) Vedolizumab (Entyvio, etc.)

*The use of high dose system corticosteroids are prohibited, with the exception of immune-related AEs (steroids can be used if not intended for treatment of AML or MDS; steroids for AML/MDS related symptoms can be used at low doses [less than 10 mg/day dexamethasone]).

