    - Bone marrow blasts decreased by  $\geq 50\%$  over pretreatment but still  $> 5\%$
    - Cellularity and morphology not relevant
  - Marrow CR: For subjects to be classified as being in marrow CR at a post-baseline visit, they must have all of the following for a minimum of 4 weeks:
    - Bone marrow:  $\leq 5\%$  myeloblasts and decrease by  $\geq 50\%$  over pretreatment
      - Peripheral blood: if HI responses, they will be noted in addition to marrow CR
  - Hematologic Improvement (HI): For subjects to be classified as having hematologic improvement (HI) at a post-baseline visit, they must have 1 measurement of the following, maintained for at least 8 weeks without ongoing cytotoxic therapy:
    - HI – erythroid:

- Hemoglobin increase of  $\geq 1.5$  g/dL or
- For RBC transfusions performed for hemoglobin  $\leq 9.0$  g/dL: reduction in RBC units transfused in 8 weeks by  $\geq 4$  units compared to the number of units transfused in the 8 weeks prior to treatment
- HI – platelets:
  - For pre-treatment platelet count of  $>20 \times 10^9$  /L platelet, absolute increase of  $\geq 30 \times 10^9$  /L
  - For pre-treatment platelet count of  $< 20 \times 10^9$  /L, platelet absolute increase of  $> 20 \times 10^9$  /L and  $\geq 100\%$  increase from pre-treatment level
- HI – neutrophils:
  - Neutrophil count increase of  $\geq 100\%$  from pre-treatment level and an absolute increase of  $> 0.5 \times 10^9$  /L
- Relapse after CR or PR: For subjects to be classified as relapsing after CR or PR requires at least one of:
  - Return to pre-treatment bone marrow blast percentage
  - Decrement of  $\geq 50\%$  from maximum response levels in granulocytes or platelets
  - Transfusion dependence or hemoglobin level  $\geq 1.5$  g/dL lower than prior to therapy
- Stable Disease (SD): For subjects to be classified as having Stable Disease (SD), they must fail to achieve at least PR but show no evidence of progression for  $>8$  weeks
- Progressive Disease (PD): For subjects to be classified as having Progressive Disease (PD), they must show blast level increases depending on prior levels as follows:
  - For patients with:
    - $<5\%$  blasts:  $\geq 50\%$  increase in blasts to  $> 5\%$  blasts
    - $5\%-10\%$  blasts:  $\geq 50\%$  increase to  $> 10\%$  blasts
    - $10\%-20\%$  blasts:  $\geq 50\%$  increase to  $> 20\%$  blasts
    - $20\%-30\%$  blasts:  $\geq 50\%$  increase to  $> 30\%$  blasts
  - Or any of the following:

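### The MDS response rules put no transfusion condition on blood counts, so transfusion alone can produce a hematologic improvement and hence an ORR response

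*Protocol*

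**What the plan says.** For MDS, Protocol 7.1.1.2 and SAP 5.1.1 give the same count rules.

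- **CR:** marrow myeloblasts of 5% or less with normal maturation, plus hemoglobin of at least 11 g/dL, platelets of at least 100 × 10⁹/L, neutrophils of at least 1.0 × 10⁹/L and no circulating blasts, for 4 weeks.
- **PR:** "they must have all CR criteria if abnormal before treatment except the following for a minimum of 4 weeks", the exception being marrow blasts that fall by at least 50% but stay above 5%.
- **Marrow CR:** blasts of 5% or less and a fall of at least 50%, with no count threshold.
- **HI:** "Requires 1 measurement of the following maintained for at least 8 weeks without ongoing cytotoxic therapy" in the protocol and "they must have 1 measurement of the following, maintained for at least 8 weeks without ongoing cytotoxic therapy" in the SAP. The erythroid limb is met by a hemoglobin rise of at least 1.5 g/dL or by a fall of at least 4 red-cell units over 8 weeks.

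None of these mentions a transfusion-free interval. AML CR in Protocol 7.1.1.1 does: transfusion independence is "defined as 1 week without RBC transfusion and 1 week without platelet transfusion", and SAP Table 1 has red-cell and platelet transfusion columns for AML.

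The primary MDS endpoint is CR + BM CR + PR. ORR (Protocol 9.4.2; SAP 5.1.6) adds HI and counts it at any post-baseline visit. SAP 6.4 makes the derived response primary and the investigator's supportive. Transfusion is expected on study: a footnote to Protocol Table 3 asks for extra laboratory checks in transfusion-dependent subjects.

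**The concern.** A transfused hemoglobin or platelet count measures the transfusion as well as the marrow. The erythroid limb of HI joins its two routes by an or, so a subject who stays on transfusion can qualify by the hemoglobin route without needing fewer units. The platelet limb has no transfusion wording at all. A programmer who follows the SAP has no basis for discounting such values.

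Each disease cohort is judged against a fixed rate with no untreated control, so nothing else separates drug effect from supportive care. At stake are the ORR estimate and, more narrowly, those CR and PR calls in the primary endpoint that depend on blood counts. HI is also one of the ways in which a subject counts as having clinical benefit for further treatment and for Observation Period 2.

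**Working it through.** **1. ORR.** Take a baseline hemoglobin of 7.5 g/dL. The threshold is 7.5 + 1.5 = 9.0 g/dL. A subject kept at 9.0 to 9.5 g/dL for 8 weeks by transfusion, with no cytotoxic therapy, meets HI-erythroid as written. No marrow change is needed, and HI alone is an ORR response. ORR has a 90% Clopper-Pearson interval and no decision threshold, so no error rate can be attached to it.

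**2. Primary endpoint.** Setting the three definitions side by side:

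| Marrow finding | Counts do not qualify | Counts qualify | Do counts change the primary result? |
|---|---|---|---|
| Blasts 5% or less, fall of at least 50% | marrow CR | marrow CR or CR | No |
| Blasts above 5%, fall of at least 50% | not a primary response | PR | Yes |
| Blasts 5% or less with normal maturation, fall under 50% | not a primary response | CR | Yes |
| None of these | not a primary response | at most HI | No |

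The third row can occur because Protocol 5.1 sets no minimum marrow blast percentage for MDS. Only rows two and three are exposed, and both need a marrow finding first. In row two, if anemia was the only abnormal count at baseline, hemoglobin held at 11 g/dL or more for 4 weeks decides PR.

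**3. Sensitivity of the MDS decision rule.** Inputs:

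- Protocol 9.1: inefficacious rate 12%, efficacious rate 25%, stated power about 0.83, type I error limit 0.10.
- Protocol 9.4.1.3: "Initially, 12 subjects will be enrolled at each dose level for each disease type during stage 1 of BOP2", then 20 and 20 more. Stop at 0 responses in 12 or at 4 or fewer in 32; success at 10 or more in 52.

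Formula, with b(n, x, p) the binomial probability and X₃ ~ Bin(20, p):

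P(success | p) = Σ over x₁ ≥ 1 and x₁ + x₂ ≥ 5 of b(12, x₁, p) · b(20, x₂, p) · P(X₃ ≥ 10 − x₁ − x₂)

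The plan's own figures come first:

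| p | Stop at 12 | Stop at 32 | Success |
|---|---|---|---|
| 0.12 | 0.2157 | 0.4646 | 0.0781 |
| 0.25 | 0.0317 | 0.0566 | 0.8348 |

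The stated power of 0.83 is reproduced, and type I error is below 0.10.

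Next, add an assumed number of percentage points of supported CR or PR to a true rate of 12%:

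| Points added | Observed rate | P(success) |
|---|---|---|
| 0 | 12% | 0.078 |
| 1 | 13% | 0.117 |
| 2 | 14% | 0.166 |
| 3 | 15% | 0.223 |
| 5 | 17% | 0.356 |

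One point is 0.01 × 52 = 0.52 of a subject in expectation. If instead 1% of true non-responders are misclassified, the rate is 0.12 + 0.88 × 0.01 = 0.1288 and P(success) is 0.112. The documents give no figure for the addition.

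**4. Can the recorded data support a rule?** SAP 6.2.5 records transfusions from 28 days before Cycle 1 Day 1 to end of treatment. An 8-week HI lasts 56 days, as long as the whole two-cycle treatment period (2 × 28 = 56), so part of it will usually fall after end of treatment. The unit-reduction limb compares with the 56 days before treatment, of which 56 − 28 = 28 lie outside the window.

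**The case against.** A reader might infer that supportive care alone can create primary responders. The documents do not support that: HI is not in the primary endpoint, and CR, marrow CR and PR each carry a marrow requirement. The remaining PR route is also narrow. The protocol speaks of red-cell transfusion given at hemoglobin of 9.0 g/dL or less, which does not suggest routine transfusion to 11 g/dL.

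A reader might also take the probabilities above as the trial's actual type I error. They are not. The added points are assumed, and nothing says how the 12% was derived. If it came from data classified by these same rules, supported responses are already in the null.

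On growth factors, a reader might infer that they are permitted because no list names them. Section 12.6.1 opens with "The following list describes concomitant medications that are prohibited" but then says the list is not exhaustive, and 6.5 and 12.6.3 bar any other MDS treatment apart from named exceptions. The most that can be said is that their status, and the handling of counts obtained on them, is unclear.

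The AML contrast is not complete either: CRi waives transfusion independence, and CRi counts in CRc. Still, the AML section says for each category whether transfusion matters, and the MDS section does not.

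Finally, transfusion dependence is a relapse criterion in the protocol, the SAP counts transfusion after a response as progression, and SAP 5.1.11 defines transfusion status separately. None of these closes the gap. ORR counts a response at any visit, no text withdraws an earlier one, and transfusion status does not feed into response.

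The limits on the primary endpoint, on the probabilities and on growth factors all stand. The gap for HI and ORR remains.

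**Conclusion.** The point holds for HI and ORR. Followed exactly, the rule classifies a transfusion-supported subject as a responder with no drug effect, which is a wrong result and not merely missing detail.

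For the primary endpoint it holds only for the count component: PR where blasts fall by at least 50% but stay above 5%, and CR where blasts are 5% or less without a 50% fall. How many subjects that would affect is unknown. The design has little tolerance: about one added percentage point takes the success probability from 0.078 to 0.117, past 0.10. That rests on an assumed addition and on the 12% null not already including such responses. The sample size, boundaries and stated power are not in question.

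**What to change.** - In Protocol 7.1.1.2, SAP 5.1.1 (MDS) and the derived response, state that hemoglobin values within 1 week after a red-cell transfusion, and platelet values within 1 week after a platelet transfusion, do not count toward CR, PR or HI. The interval is the protocol's own, from AML CR.
- For visits after end of treatment, either extend transfusion recording through the observation periods or flag the response as not confirmed transfusion-free. SAP 5.1.11 already defines transfusion status to the end of Observation Period 2, so 6.2.5 needs to agree with it in any case.
- State how counts obtained on hematopoietic growth factors enter the response derivation, and reconcile that with the ban on other MDS treatments in Protocol 6.5 and 12.6.
- Separately, reconcile the 8-week pre-treatment comparison in the unit-reduction limb with the 28-day recording window. Until that is done, subjects transfused at baseline should not be confined to that limb, since half of the comparison period would be unrecorded.

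The cost is one protocol sentence, SAP text and programming, and a modest extension of transfusion recording. Some visits will not count, and a few subjects may move from PR or HI to stable disease. The change affects endpoint derivation only, not how subjects are treated.

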7.1.1.3 Hematology Laboratory Assessments

Primary endpoints of hematology clinical laboratory tests will be performed at every visit. Refer to [Section 9.4.1 Analysis of Primary Endpoint] for definitions of CRc for subjects with R/R AML and CR + BM CR + PR for R/R higher risk MDS.

Secondary endpoints of hematology clinical laboratory tests will be performed at every visit. Refer to [Section 9.4.1 Analysis of Primary Endpoint] for definitions of duration of remission, event-free survival (EFS), OS, CR, BM CR, best response, CRh, HI, and objective response.

7.1.2 Bone Marrow Aspirations and/or Biopsies

Study procedures and their timing are summarized in the Schedules of Assessments [Table 1 and Table 2]. After the completion of Observation Period 1 (8 weeks), subjects remaining in the study, because they achieved remission (CRc or PR for AML subjects and CR, BM CR, PR, or HI for MDS subjects) or have clinical benefit as determined by investigator, will have bone marrow samples collected in Observation Period 2 every 3 months or if there is suspicion of relapse in the whole blood. If bone marrow aspirate is unobtainable (e.g., dry tap), an additional ethylenediaminetetraacetic acid tube of whole blood should be collected instead. Bone marrow aspirate is required, and bone marrow biopsy is preferred. In case of inadequate aspirate, bone marrow biopsy is required. Samples must be submitted to a central laboratory for analysis. Please refer to the laboratory manual for additional information.

7.2 Safety Assessments

Study procedures and their timing are summarized in the Schedules of Assessments [[Table 1](#) and [Table 2](#)]. Protocol waivers or exemptions are not allowed.

Procedures conducted as part of a subject's routine clinical management (i.e., standard of care) obtained before signing the ICF may be utilized for screening or baseline purposes, provided the procedures met the protocol-specified criteria and were performed within the timeframe, as defined in the Schedules of Assessments [[Table 1](#) and [Table 2](#)].

7.2.1 Adverse Events

See [Section [7.3](#) Adverse Events and Other Safety Aspects] and [Section [12.4](#) Adverse Events: Definitions and Procedures for Recording, Evaluating, Follow-up and Reporting] for information regarding AE collection and data handling.

7.2.2 Laboratory Assessments

- See [Appendix [12.7](#) Laboratory Assessments] for the list of clinical laboratory tests to be performed and refer to the Schedules of Assessments [[Table 1](#) and [Table 2](#)] for timing and frequency.
- Laboratory samples will be analyzed by the institution's local laboratory. However, ONLY local sample results must be submitted for centralized data entry. Refer to the laboratory manual for additional information.
- Additional laboratory tests should be performed according to institutional standard of care.
- Local testing of bone marrow aspirate and/or biopsy will be reported in the eCRF; however, samples must also be submitted to a central laboratory for analysis. Refer to the laboratory manual for additional information.
- The investigator or subinvestigator must review the laboratory report and document this review.
- Clinical significance of out-of-range laboratory findings is to be determined and documented by the investigator or subinvestigator who is a qualified physician.

7.2.3 Vital Signs

Blood pressure, radial pulse rate and body temperature will be measured as specified in the Schedules of Assessments [[Table 1](#) to [Table 2](#)]. Blood pressure should be measured prior to other clinical assessments. Whenever possible, the blood pressure determinations should be undertaken at approximately the same time of day for each study visit.

A calibrated blood pressure measuring device should be used for all blood pressure measurements.

Prior to measuring blood pressure, the study subject should be seated in a quiet room for at least 5 minutes, with his/her back supported and feet comfortably resting on the floor.

